6.15.1. Adverse Event Reporting

Patients will be instructed to report all AEs, which can be reported at any time. AEs that occur from ICF signature until the time of administration of the first dose of etrasimod will be regarded as ‘pre-treatment’ and recorded as an AE. All events reported following study medication administration up to 30 days after the last medication intake will be presented as treatment emergent AEs (TEAEs).

Monitoring of ongoing AEs will be continued up to 30 days after study medication administration.

[figure not shown]
For this study, an AE is defined as: “Any untoward medical occurrence in a study patient administered etrasimod which does not necessarily have to have a causal relationship with this treatment.” An AE can therefore be any unfavorable and unintended sign (including an abnormal

laboratory finding), symptom, or disease temporally associated with the use of the study medication, whether or not related to the product. AEs can be any of the following:

- Unfavorable changes in general condition
- Subjective or objective signs/symptoms
- Concomitant disease or accidents
- Clinically relevant adverse changes in laboratory parameters observed in a patient in the course of a clinical study
- Pre-existing conditions which worsen in severity or frequency or which have new signs/symptoms associated with them

Lymphopenia will not be captured as an AE because it is an expected pharmacologic effect of the drug.

AEs will be elicited at the time indicated in the schedule. Any adverse or unexpected events, signs and symptoms will be fully recorded on the AE Form including details of intensity, onset, duration, outcome and relationship to the drug as determined by the PI. Whenever possible, a constellation of signs and symptoms should be recorded as a unifying diagnosis (e.g., self-limited fever, runny nose, cough, and scratchy throat should be captured as an upper respiratory infection rather than by the individual signs and symptoms). AEs may also be reported at any time. The type and duration of follow-up of patients after AEs will be documented.

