6.9. Clinical Laboratory Tests

The clinical laboratory tests will be performed as outlined in Schedule of Procedures and Visits (Table 1). Tests will be performed in the central laboratory. If the patient lives in a remote area, laboratory testing for close observation for possible DILI may be performed locally and the results promptly communicated to the clinic.

In the event of abnormal clinical laboratory values, the physician will make a judgment whether or not the abnormality is clinically significant. If clinically significant, it will be captured and recorded as an AE.

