6.19. Study and Site Discontinuation

The sponsor has the right to terminate this study at any time. Reasons for terminating the study may include, but are not limited to, the following:

- The incidence or severity of AEs in this or other studies indicates a potential health hazard to patients.
- Patient enrollment is unsatisfactory.

Additionally, if more than three patients develop a CTCAE Grade 3 or higher event in the same category, or if three or more patients meet one of the individual stopping rules, the safety and dose escalation review committee (5.5) will convene to evaluate the findings. Further, dosing will be stopped in randomized patients and no new patients will be randomized until the safety and dose escalation review committee reviews and evaluates the findings.

The sponsor will notify the investigator and IEC if the study is placed on hold, or if the sponsor decides to discontinue the study or development program.

The sponsor has the right to replace a site at any time. Reasons for replacing a site may include, but are not limited to, the following:

- Excessively slow recruitment
- Poor protocol adherence
- Inaccurate or incomplete data recording
- Non-compliance with the ICH guidelines for GCP

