9.2. Sample Size and Power Calculations

There is no formal sample size estimation for this proof-of-concept open label study. A sample size of 20 subjects is reasonable to assess the efficacy and safety of etrasimod in the target population.

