9.7. Safety Analysis

Safety and tolerability will be assessed by a review of all safety parameters including AEs, laboratory safety parameters, [REDACTED] vital signs, and ECG. AEs will only be presented as summary tabulations. When assessing change from baseline, a baseline measurement is also required. Baseline for the safety analysis is defined as the average of the pre- dose measurements. No missing data will be imputed for the safety analysis. For continuous variables, summary statistics (N, mean [or median], SD, mean [or median] change/percent change) and 95% CI will be produced if applicable; for proportion-based measures, N, frequencies, proportion and its 95% CI will be produced.

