9.7.6. Clinical Laboratory Values

Individual lab values will be listed by visit, and summarized using descriptive statistics. Summary statistics will also be provided for change from baseline in hematological parameters (e.g., lymphocytes) or other parameters. Baseline is defined as the average of the pre-dose measurements. A clinically significant change from baseline may be recorded as an AE if deemed appropriate by the PI or sponsor.

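### Section 6.15.1 bars lymphopenia of any grade from AE capture, in conflict with 6.9, and no count of patients by worst lymphocyte grade is planned

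*Combined protocol and SAP*

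**What the plan says.** The sections that bear on lymphopenia are:

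- **6.15.1 (AE reporting).** The list of what counts as an AE includes "Clinically relevant adverse changes in laboratory parameters observed in a patient in the course of a clinical study". Shortly after that list comes the exclusion: "Lymphopenia will not be captured as an AE because it is an expected pharmacologic effect of the drug". It has no limit by grade, duration, seriousness or effect on treatment.
- **6.9 (laboratory tests).** The physician judges whether an abnormal value is clinically significant. "If clinically significant, it will be captured and recorded as an AE". Lymphocytes are not excepted.
- **6.15.2 (SAEs).** Blood dyscrasias are among the examples of important medical events that may be serious.
- **9.7.6 (laboratory analysis).** Individual values are listed by visit. "Summary statistics will also be provided for change from baseline in hematological parameters (e.g., lymphocytes) or other parameters". The section ends: "A clinically significant change from baseline may be recorded as an AE if deemed appropriate by the PI or sponsor".
- **9.5 and 9.6.1.** Blood counts, including lymphocytes and subsets, are endpoints at Weeks 12 and 24, summarised with mean, median, range and SD.
- **6.12.1.** A patient whose lymphocyte count is neither back to 80% of baseline nor within normal range at Week 26 returns for weekly counts until it is.
- **6.15.3 and 6.19.** CTCAE v4.03 grades are assigned to AEs. The review committee convenes and dosing pauses "if more than three patients develop a CTCAE Grade 3 or higher event in the same category", or if three or more patients meet an individual stopping rule.

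**The concern.** Safety and tolerability form the only primary objective (2.1), and lowering circulating lymphocytes is how the drug is meant to work (1.2, 1.3.1). An effect can be expected and still be severe in some patients. The exclusion is justified by expectedness alone, and it removes every degree of severity from the AE record.

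Three things are at stake. First, two sites could treat the same patient differently, one following 6.9 and the other 6.15.1, and each would be following the protocol. This matters most for a case that is serious or ends treatment. Second, a reader of the AE tables would see no lymphopenia, and no other planned table gives the number of patients who reached each grade. Third, it is not stated whether lymphopenia counts towards the pause in 6.19.

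**Working it through.** The plan gives no figure to reproduce: there are no hypothesis tests (9.1), and "There is no formal sample size estimation for this proof-of-concept open label study". The check is mainly a comparison of the text.

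**Step 1: is there a conflict?**

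| Section | Rule for a clinically significant low lymphocyte count | Against 6.15.1 |
|---|---|---|
| 6.15.1, exclusion | Not an AE | – |
| 6.9 | Must be recorded as an AE | Direct conflict |
| 6.15.1, general list | Falls within the AE definition | Conflict, unless the exclusion is read as an exception |
| 6.15.2 | Could be serious, as a blood dyscrasia | Unclear |
| 9.7.6 | May be an AE at the PI's or sponsor's discretion | Weak: permits what 6.15.1 forbids |

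No visible section gives an order of precedence.

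**Step 2: what do the outputs show?** Section 9.7 says "AEs will only be presented as summary tabulations", and 9.7.1 adds listings by patient. Both draw on captured AEs, so under 6.15.1 neither would contain lymphopenia. Outside the AE system, the plan gives listings by visit, change from baseline, and the range at Weeks 12 and 24. The range shows the lowest value at those two visits. It does not show how many patients reached a given grade at any visit. Non-recovery at Week 26 triggers repeat sampling under 6.12.1, but no tabulation of it is described.

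**Step 3: does it reach the pause count?** The first limb of 6.19 counts CTCAE Grade 3 or higher events. Grades are assigned to AEs (6.15.3), so the natural reading is that it counts graded AEs; lymphopenia then contributes 0. The second limb refers to individual stopping rules. Those visible in 5.2.1 concern ECG changes and DILI, not lymphocytes.

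**Step 4: would counting it matter?** Inputs: n = 20 (the maximum sample size), and more than three patients means at least 4 (4/20 = 20%). The true Grade 3 or higher rate p is not in the documents, so it is an assumption, varied from 5% to 60%. Taking lymphopenia as one category and patients as independent:

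P(X ≥ 4) = 1 − Σ(k = 0 to 3) C(20,k) p^k (1−p)^(20−k)

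At p = 0.20 the four terms are 0.0115 + 0.0576 + 0.1369 + 0.2054 = 0.4114, so P = 1 − 0.4114 = 0.5886.

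| Assumed p | Trigger met if lymphopenia counts | Contribution if excluded |
|---|---|---|
| 5% | 1.6% | 0 |
| 10% | 13.3% | 0 |
| 20% | 58.9% | 0 |
| 30% | 89.3% | 0 |
| 40% | 98.4% | 0 |
| 50% | 99.9% | 0 |
| 60% | >99.9% | 0 |

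**Step 5: what would a graded table add?** For proportions in the safety analysis, 9.7 already plans the frequency, proportion and 95% CI. With exact (Clopper–Pearson) limits, 4 of 20 patients would be reported as 20% (5.7% to 43.7%) and 10 of 20 as 50% (27.2% to 72.8%). These intervals are wide, but this is the patient-level severity information that the current outputs lack.

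**The case against.** The strongest reply is that 6.15.1 is a deliberate, reasoned exception. It comes shortly after the general AE list, and a specific exception ordinarily qualifies a general rule such as 6.9. This is a fair account of the probable intent. But the protocol does not say it, and intent does not settle what to do with a case that is serious or ends treatment.

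On 9.7.6 the reply is largely right. The mention of lymphocytes illustrates the change-from-baseline summary, and the later AE sentence is only permissive. That section needs alignment; it is not a second direct contradiction.

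Three stronger readings are tempting, and the documents do not support them:

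- *The lymphocyte effect is hidden from the study.* It is not. With at most 20 patients, a listing by visit exposes every low count; median and range are planned at two visits, and patients who have not recovered are followed weekly. Infections and other clinical consequences remain reportable AEs.
- *Lymphopenia can never count in 6.19.* That section says event, not AE, and defines neither event nor category. Non-counting is the natural reading, but it is an inference.
- *All patients could have lymphopenia while the table shows 0 of 20.* That is a logical maximum. The documents give no rate.

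It can also be said that keeping an expected pharmacologic effect out of a dosing pause is a defensible choice, since at moderate rates the pause would be likely (58.9% at an assumed 20%). That stands as an argument about the choice. It does not remove the need to state the choice.

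**Conclusion.** The point holds as a conflict in recording rules and a gap in the safety tables. Sections 6.15.1 and 6.9 give opposite instructions for a clinically significant low lymphocyte count; 6.15.2 leaves the serious case unclear, and 9.7.6 adds a weaker inconsistency. Followed as written, 6.15.1 puts no lymphopenia in the AE tables that serve the primary objective, and the visible text plans no count of patients by worst grade.

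The effect on the pause count is conditional on reading an event in 6.19 as a captured, graded AE. On that reading the contribution is 0 at any true rate. If lymphopenia were counted, the chance of meeting the trigger would be 1.6% to above 99.9% over the assumed 5% to 60%, and more likely than not at 20%. This range shows only that the answer is material; it does not predict what this drug will do. The conclusion about tables rests on the visible text, since parts of the protocol are redacted.

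**What to change.** **Wording.** Reconcile 6.15.1, 6.9, 6.15.2, 9.7.6 and 6.19 so that they agree on whether lymphopenia that is serious or stops treatment is recorded, and on whether lymphopenia counts in 6.19. Both are clinical decisions for the sponsor, and no rule is proposed here. A cross-reference between 6.9 and 6.15.1 should state which governs.

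**Analysis.** Add to 9.7.6:

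- The number and proportion of patients, with 95% CI, by worst post-baseline lymphocyte count in CTCAE v4.03 grades, by dose level. State the cut-points, because 6.15.3 reproduces only the general grade definitions. Assign each count to the dose being taken when it was drawn. Show the length of exposure, because patients who do not escalate spend 24 weeks on 1 mg and escalated patients have one extra visit.
- The number of patients not recovered at Week 26 by the 6.12.1 definition, stating which baseline is used.

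**Cost.** One wording change and one extra table. Blood counts are already drawn at every treatment and follow-up visit listed in 7.2 and 7.3, so no sampling is added and the sample size is unaffected. The small downside is that a high lymphopenia rate, if it occurs, will be plainly visible and will need to be explained as pharmacology.

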6.15.2. Serious Adverse Events and Expedited Reporting of Adverse Events

An SAE is any untoward medical occurrence that at any dose results in the following outcomes:

- Death
- Is life-threatening
- Required/Prolonged hospitalization
- Disability/Incapacity
- Congenital anomaly/birth defect

- Important medical event

SAEs will be captured from the time of ICF signature to 30 days after the last dose of study drug, and will be monitored until resolution or stabilization.

An important medical event that may not result in death, be life-threatening, or require hospitalization may be considered a SAE when, based upon appropriate medical judgment, it may jeopardize the patient and may require medical or surgical intervention to prevent one of the outcomes listed in this definition. Examples of such a medical event includes allergic bronchospasm requiring intensive treatment in an emergency room or at home, blood dyscrasias, or convulsions that do not result in in-patient hospitalization, or the development of drug dependency or drug abuse.

Elective hospitalization and/or surgery for clearly pre-existing conditions (for example a surgery that has been scheduled prior to the patient's entry into the study) will not be reported as a SAE. All other hospitalizations, including elective hospitalizations for any condition that was not pre-existing, will be reported as a SAE.

Any AE considered serious by the investigator or which meets SAE criteria must be reported to PPD Pharmacovigilance (PVG) within 24 hours from the time study site personnel first learn about the event.

The following contact information is to be used for SAE reporting:

EMEA ASIA Safety Central Mailbox: [REDACTED]

Australia: [REDACTED] (tel)

Australia: [REDACTED] (fax)

Or alternatively:

PPD Medical Affairs/Pharmacovigilance

PPD PVG Hotline: (United Kingdom number) [REDACTED] PPD PVG

Fax line: (United Kingdom number) [REDACTED]

A full description of every SAE will need to be provided to PPD PVG (this may be supported by source documentation such as laboratory reports or a discharge summary should the patient be hospitalized).

Other safety issues as defined in ICH Guideline E2A, and EU Eudralex Volume 10 also qualify for expedited reporting. In these situations, the process will be as detailed for SAEs above:

- SAEs which could be associated with the trial procedures;
- SAEs and AEs of special interest that could materially influence the benefit-risk assessment of a medicinal product, such as: a clinically important increase in the rate of a serious suspected adverse reaction over that listed in the investigator brochure.

6.15.2.1. Patient and Patient-Partner Pregnancy

Patients who become pregnant during the study will be discontinued immediately. Although not considered an SAE or AE, pregnancies occurring during the period of study drug administration

(Day 1 to Week 24) until 30 days after the last dose of study drug should be reported to the sponsor contact and IEC in the same manner as an SAE.

Pregnancies will be followed every trimester through the first well baby visit. For female partners whom become pregnant by male study patients during the course of the study, reasonable efforts will be made to collect information on the partner's pregnancy through the first well baby visit as provided by the male study patient.

6.15.3. Assessment of Adverse Event Severity

The severity of each AE will be assessed at onset by a nurse and/or physician. When recording the outcome of the AE the maximum severity of the AE experienced will also be recorded. The severity of the AE will be graded according to the CTCAE v4.03³¹ definitions, listed below:

Grade 1: Mild; asymptomatic or mild symptoms; clinical or diagnostic observations only; intervention not indicated.

Grade 2: Moderate; minimal, local or noninvasive intervention indicated; limiting age-appropriate instrumental Activities of Daily Living (ADL)*.

Grade 3: Severe or medically significant but not immediately life-threatening; hospitalization or prolongation of hospitalization indicated; disabling; limiting self-care ADL**.

Grade 4: Life-threatening consequences; urgent intervention indicated.

Grade 5: Death related to AE.

Activities of Daily Living:

*Instrumental ADL refer to preparing meals, shopping for groceries or clothes, using the telephone, managing money, etc.

**Self-care ADL refer to bathing, dressing and undressing, feeding self, using the toilet, taking medications, and not bedridden.

6.15.4. Assessment of Adverse Event Relationship to Study Medication

The relationship of an AE to investigational product(s) will be classified using modified WHO criteria (Edwards and Biriell, WHO Collaborating Centre for International Drug Monitoring 1994) as follows:

Related: a clinical event, including laboratory test abnormality, with a reasonable time sequence to administration of the drug, unlikely to be attributed to concurrent disease or other drugs or chemicals, and which follows a clinically reasonable response on withdrawal. Re-challenge information is not required to fulfill this definition; or an event that could also be explained by concurrent disease or other drugs or chemicals where information on drug withdrawal may be lacking or unclear.

Not related: a clinical event, including laboratory test abnormality, with sufficient evidence to accept that there is no causal relationship to drug administration (e.g., no temporal relationship to drug administration, because the drug was administered after onset of event; investigation shows that the drug was not administered; proof of other cause; etc.); or an event with a temporal relationship to drug administration which makes a causal relationship improbable, and in which other drugs, chemicals or underlying disease provide plausible explanations.

6.15.5. Assessment of Adverse Event Outcome

Outcome of AEs will be defined according to ICH Guideline E2B.

- Recovered/Resolved
- Recovered/Resolved with sequelae
- Recovering/Resolving
- Not recovered/not resolved
- Fatal
- Unknown

6.15.6. Action Taken for Adverse Event

Action taken for AEs will be documented according to the following:

- Concomitant medication or other treatment
- Withdrawal from the study

6.15.7. Action Taken for Study Drug

Any action taken with study drug will be defined according to ICH Guideline E2B and documented in the CRF according to the following:

- Drug withdrawn
- None (not changed)
- Dose interrupted
- Unknown
- Not applicable

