1.3.2. Rationale for Study Design

This is an open-label, multicenter, dose escalation study to evaluate the safety, tolerability, PK and efficacy of two oral etrasimod daily doses (1 mg and 2 mg) for a total of 24 weeks (12 weeks at each dose level) in up to 20 patients with early stage PBC. In each patient, 1 mg daily will be evaluated initially for 12 weeks followed by a potential dose escalation to 2 mg daily based on each individual patients' safety and PK data. The open-label nature of the study allows for each subject to be evaluated closely for dose escalation based on their safety and PK data. The pharmacological activity and efficacy of etrasimod will also be evaluated. Clinically, PBC is monitored by assessing biochemical markers primarily, ALP levels, and other liver enzymes including gamma- glutamyltransferase (GGT) and bilirubin. Given the nature of these measures it is reasonable to plan an initial evaluation of clinical response without inclusion of placebo controls in this study.

A 3-month (12-week) treatment period for each dose level was chosen to assess the safety, efficacy and pharmacodynamic activity in patients. This timeframe is judged appropriate to establish an initial safety and clinical effect of etrasimod in PBC patients. Although this study is only including patients with early stage of PBC disease, it is possible that clearance of etrasimod may be decreased and systemic exposure increased. For this reason, the study was designed to assess the PK of the low dose (1 mg) after the initial dose on Day 1 and on Week 2 (i.e. steady-state) in each patient prior to allowing a dose escalation to 2 mg at Week 12.

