2. STUDY OBJECTIVES

2.1. Primary Objectives

Safety

- To assess the safety and tolerability of etrasimod in patients with PBC.

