5.2. Dosage, Administration and Accountability

Investigational product will be dispensed to the patients under the supervision of the investigator or his/her designee; 1 mg or 2 mg tablet p.o., based on available PK and safety data (vital signs and ECG). [REDACTED]

Investigational product will be dispensed as follows:

- [REDACTED] The responsible investigator or designee at clinic will dispense tablets as appropriate. Patient will return the bottle with all remaining tablets [REDACTED].
- [REDACTED] Patient will return the bottle with all remaining tablets [REDACTED].
- [REDACTED] Patient will return the bottle with all remaining tablets [REDACTED].
- [REDACTED] Patient will return the bottle with all remaining tablets [REDACTED].
- [REDACTED] Patient will return the bottle with all remaining tablets [REDACTED].
- [REDACTED] Patient will return the bottle with all remaining tablets [REDACTED].
- [REDACTED] Patient will return the bottle with all remaining tablets [REDACTED].

The investigator will maintain accurate records of the receipt of all study medication. In addition, accurate records will be kept regarding when and how much study medication is dispensed and used by each patient in the study.

Investigational product accountability will be performed by the site [REDACTED]

Reasons for deviation from the expected dispensing regimen must also be recorded. Study medication will be reconciled by the sponsor's monitor or contracted designee. The investigator agrees to provide sufficient access to study medication as required for the reconciliation process to be completed in a timely fashion.

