5.2.1. Dose-stopping Rules

Any of the following findings in a patient during treatment will lead to a stop in etrasimod dosing in the affected patient:

- Certain ECG changes (see details 6.6), or
- Clinical evidence of drug-induced liver injury (DILI; as described in 6.15)

As described in 3.1, at the discretion of the PI, the dose of etrasimod may be adjusted from 2 mg q.d. back to 1 mg q.d. if deemed necessary. If the patient is on 1 mg, the PI may discontinue etrasimod treatment if deemed necessary based on the dose-stopping rules.

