8.2. Data Coding

8.2.1. Adverse Events

AEs will be coded using the most current Medical Dictionary for Regulatory Activities (MedDRA) and tabulated, including categorical information of interest such as onset and resolution times, time of onset relative to dose, severity at onset, maximum severity, causal relationship to study medication, and action taken. Whenever possible, a constellation of signs and symptoms should be recorded as a unifying diagnosis (e.g., self-limited fever, runny nose, cough, and scratchy throat should be captured as an upper respiratory infection rather than by the individual signs and symptoms). AEs will be regarded as 'pre-treatment' if they occur between screening and the time of administration of the first dose of etrasimod. All other AEs that occur after the first dose of study medication will be considered to be 'treatment-emergent'.

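### The study-drug action list has no entry for the permitted 2 mg to 1 mg reduction, and the readable analysis text does not separate Week 24 efficacy or AEs by dose taken

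*Combined protocol and SAP*

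**What the plan says.** **Dose changes.** Section 5.2.1 provides that, at the investigator's discretion, "the dose of etrasimod may be adjusted from 2 mg q.d. back to 1 mg q.d. if deemed necessary". The synopsis carries the same provision. Escalation at Week 12 is decided patient by patient (section 7.2.4), and patients who do not escalate stay on 1 mg to Week 24 (section 3.1).

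**Recording.** Section 6.15.7 states: "Any action taken with study drug will be defined according to ICH Guideline E2B and documented in the CRF according to the following". Its five entries are withdrawn, not changed, interrupted, unknown and not applicable. Section 6.15.6 has a second list, introduced by "Action taken for AEs will be documented according to the following", with two entries: medication or other treatment given, and withdrawal from the study. Under section 5.2, "accurate records will be kept regarding when and how much study medication is dispensed and used by each patient in the study", and reasons for departing from the expected dispensing regimen must also be recorded.

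**Analysis.** The primary objective (section 2.1) is "To assess the safety and tolerability of etrasimod in patients with PBC". Sections 8.2.1 and 9.7.1 tabulate AEs by several attributes, including "time of onset relative to dose, severity at onset, maximum severity, causal relationship to study medication, and action taken". Section 1.3.2 says the study is to "evaluate the safety, tolerability, PK and efficacy of two oral etrasimod daily doses (1 mg and 2 mg"). Sections 9.5 and 9.6.1 summarise ALP change to Weeks 12 and 24, with 95% CIs, and name no dose grouping. The Statistical Analyses part of the synopsis splits AEs and laboratory data between treatment period and follow-up period. Section 6.15.1 says events "up to 30 days after the last medication intake will be presented as treatment emergent AEs (TEAEs"), whereas sections 8.2.1 and 9.7.1 count any AE after the first dose and state no end.

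**The concern.** Stepping down from 2 mg because of an AE is a tolerability result, and tolerability is half of the primary objective. If the CRF offers only the five listed actions, the site must choose a label that does not describe what happened, and the table of AEs by action taken inherits the error. With up to 20 patients, one or two such cases would alter how that table reads.

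The second issue is one of reporting. By Week 24 the patients may be a mixture of 1 mg throughout, escalated to 2 mg, and escalated then reduced. A single Week 24 mean depends on how many patients are in each group. Section 9 intends to set such results beside historical data, but the plan does not ask for the numbers escalated or reduced to be shown with them. AE counts pooled over 24 weeks would likewise say little about 2 mg specifically.

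**Working it through.** The plan states no power or precision figure on this point, so there is nothing to reproduce. The check is mainly a comparison of passages.

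**1. Actions permitted against actions recordable.**
- Permitted by the design: escalation, reduction from 2 mg to 1 mg, stopping.
- Recordable under 6.15.7: withdrawn, not changed, interrupted, unknown, not applicable. Entries that describe a reduction: 0 of 5.
- Recordable under 6.15.6: other treatment, withdrawal from the study. Entries that describe a reduction: 0 of 2.
- Whichever list supplies the action-taken attribute in 8.2.1 and 9.7.1, the table has no row for a reduction.
- Related: 5.2.1 refers to 3.1 for this reduction, but the readable text of 3.1 does not describe it. The visit list in 7.2.6 has dispensing lines only for patients who escalate (2 mg) and those who do not (1 mg). These passages need to be reconciled with 5.2.1; no view is taken on the clinical rule.

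**2. Dose grouping in the analysis text.** Sections 9.3, 9.5 and 9.6.1 contain no grouping by dose taken. The subgroups readable in 9.6.2 do not include dose taken. The only analysis explicitly by dose level is the PK plots in 9.6.3. The Week 12 efficacy summary is unaffected, since escalation starts only at Week 12.

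**3. Meaning of the treatment period.** Sections 3.1, 3.2 and the heading of 7.2 use the term for the full 24 weeks. Sections 1.3.2 and 3.2 also use it for each 12-week dose block. No readable passage says which sense governs the AE tabulation. The plainest reading, matching the headings of 7.2 and 7.3, is 24 weeks against follow-up, which pools AEs across doses.

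**4. How much exposure is at 2 mg.** The documents give no escalation rate. Assume k of 20 patients escalate, all complete 24 weeks without interruption, and none is reduced.
- On-drug patient-weeks: 20 × 24 = 480.
- At 2 mg: 12 × k.
- k = 5: 60/480 = 12.5%. k = 10: 120/480 = 25%. k = 15: 180/480 = 37.5%. k = 20: 240/480 = 50%.
- Any reduction lowers the 2 mg share, so 50% is the ceiling under these assumptions. These are exposure shares, not dose effects.

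**5. Precision of results by sequence.** The half-width of a 95% CI for a mean change, in SD units, is t(0.975, n−1)/√n.
- n = 20: 2.093/4.472 = 0.468.
- n = 10: 2.262/3.162 = 0.715.
- n = 5: 2.776/2.236 = 1.242.

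**The case against.** **E2B.** Section 6.15.7 defers to ICH E2B, and the CRF itself is not among the documents, so the category may already exist in practice. This makes the harm conditional, but it does not remove the mismatch: 6.15.7 prescribes its own list for the CRF, and that list is incomplete.

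**Other records.** A reader might infer that AE-driven reductions would be lost altogether. The documents do not support that. Section 5.2 requires records of how much drug each patient uses, and reasons for departures from the expected dispensing regimen, which would include a reduction if it counts as such a departure. Section 9.7.1 also lists AEs by patient. The loss is confined to the planned action-taken table.

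**The pooled Week 24 result.** It is tempting to call it invalid. It is not: it describes the regimen of 1 mg with possible escalation, the objectives concern etrasimod rather than each dose, and no hypothesis is tested. Nor can one say that the plan contains no dose split. The synopsis statistics and 9.6.2 have redactions where one could sit, and the 9.6.2 list is open-ended. The absence claim reaches only the readable text.

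**AEs.** A reader might assume a cut at Week 12, leaving a second half of mixed doses. No passage describes such a cut. What can be said is that the term has two senses and the tabulation does not choose between them.

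**Small, selected groups.** Splitting at most 20 patients by a post-baseline dose decision gives imprecise groups selected on safety and PK. That stands, and limits the added tables to description.

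**Conclusion.** The gap in the action list is an error in the text as written and should be corrected. Section 5.2.1 and the synopsis permit a change that 6.15.7 cannot record, and the AE table depends on that record. Its numerical effect is unknown, because the documents give no expected number of reductions; its consequence is a missing link between AE and reduction, recoverable from drug records.

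The lack of dose grouping is a low-cost improvement, not a flaw that invalidates an analysis. It rests on the stated aim of evaluating both doses and on readable text only. Under the completion assumption above, 2 mg accounts for no more than 50% of on-drug patient-weeks, so tables pooled over the 24 weeks would be at least half 1 mg experience. Results by dose sequence would not amount to a comparison of doses.

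**What to change.** 1. Reconcile 6.15.7 with 5.2.1 by adding a 'dose reduced' category to the study-drug action list. This concerns data capture only.
2. Keep the pooled Week 24 summary and state beside it the numbers of patients escalated and reduced.
3. Add Week 24 ALP change by actual dose sequence: 1 mg throughout; 1 to 2 mg; 1 to 2 to 1 mg. If a paired Week 12 to Week 24 change is shown for escalated patients, say whether reduced patients are included. Label it non-randomised, selected on safety and PK, and confounded with time on treatment.
4. Add treatment-emergent AEs by dose at onset, with patient-weeks at each dose. First settle one treatment-emergent window, since 6.15.1 differs from 8.2.1 and 9.7.1, and state in advance how events after the last intake are assigned.
5. State which sense of the treatment period applies to the AE tabulation in the synopsis, and carry it into section 9.7.

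The cost is one CRF category, a few sentences, and descriptive tables from data already collected. The drawback is wide intervals: about 1.24 SD either side in a group of 5.
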